5.2 Secondary study parameters

The secondary end points of this trial will be tested in the same manner as described for the primary end point. Additionally, the secondary objectives will be assessed with the appropriate tests for the different objectives.

5.3 Other study parameters

Multivariate analyses will be performed to assess possible associations with surgeon experience, geographical differences and risk factors for complications after surgery.

5.4 Handling missing and spurious data

When missing data occurs in the primary outcome variable, a sensitivity analysis will be performed. In the sensitivity analysis, the missing data at three months will be substituted by the value "recurrence", unless the result at later follow up is "no recurrence". Missing data at twelve months will be substituted by the value "recurrence", unless the result at later follow up is "no recurrence". Missing data at three years will be substituted by the value "recurrence". In the analyses of secondary objectives, analyses will be carried out on available data, with reporting of proportions of missing data.

All analyses will be performed using software SPSS 20, Stata 13 and R 3.0 or higher. Analysis will be based on the principle of intention-to-treat. All patients who signed the

informed consent form, met the study entry criteria and underwent randomization will be included in the analysis.

Results will be presented in tables reporting at least the number of subjects, mean, standard deviation, minimum and maximum for continuous data; and number of subjects and percentages for categorical data.

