3. METHODS

3.1 Study parameters/endpoints

3.1.1 Main study parameter/endpoint

- Comparison of the proportions of Arm A and Arm B subjects who undergo TURB for a Ta, T1 or CIS bladder tumor that have a histologically confirmed recurrence found at either three months, one year and three years after TURB.

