5. STATISTICAL ANALYSIS

5.1 Primary study parameters

The primary end point will be analysed by testing the following hypothesis.

The proportions of patients in either Arm A or Arm B who have recurrence of bladder cancer at one year after TURB will be compared. A two-sided test will be used, with the accompanying null-hypothesis being:

H_0 : The proportions of subjects with recurrence of bladder cancer at one year after TURB are equal for Arm A and Arm B, i.e. $H_0: \pi_A = \pi_B$;
with subsequently, $H_1: \pi_A \neq \pi_B$.

An intention-to-treat analysis will be performed, meaning that all subjects who were randomized will be included in the analyses.

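### The sensitivity rule for a missing 12-month result ignores earlier visits, so it can overwrite a confirmed recurrence, and it never tests loss that counts against SPIES alone

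*Protocol*

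**What the plan says.** Section 5.4 makes the rule conditional and limits it to a sensitivity analysis: "When missing data occurs in the primary outcome variable, a sensitivity analysis will be performed". For the 12-month outcome, "Missing data at twelve months will be substituted by the value" recurrence, with one exception: a later follow-up result of no recurrence. The 3-month rule has the same form. The 3-year rule has no exception: "Missing data at three years will be substituted by the value" recurrence. No rule refers to a result seen before the missing visit.

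Section 5.1 gives the primary comparison: "The proportions of patients in either Arm A or Arm B who have recurrence of bladder cancer at one year after TURB will be compared". It calls the analysis intention-to-treat, "meaning that all subjects who were randomized will be included in the analyses". Section 3.1.1 words the endpoint as "histologically confirmed recurrence found at either three months, one year and three years after TURB".

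Sections 3.4.3 to 3.4.5 schedule white-light cystoscopy at 3, 6, 9, 12, 18, 24, 30 and 36 months, and ask for histology on every visible lesion. A recurrence can therefore be confirmed, and recorded, at three visits before month 12.

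**The concern.** An imputation rule should fill in what is unknown and leave what was observed alone. This one looks only forward, which causes two classification problems.

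- **Erasure.** A patient with a confirmed recurrence at month 6 is treated, misses month 12 and is clear at month 18. The literal text scores no recurrence at 12 months, against observed histology.
- **Back-dating.** A patient is clear at month 9, misses month 12 and has no clear result afterwards. That patient is scored as a 12-month event, even if the first recurrence is found well after month 12.

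A third problem concerns what the check can show. Every gap without a later clear visit becomes an event in both arms. The assumption is the same for each arm, so the analysis does not ask whether a SPIES benefit survives if the patients lost from Arm A did worse than those lost from Arm B. A reader of the trial would want to know that.

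**Working it through.** **Inputs.** From section 2.5: control recurrence 35% at one year, a relevant difference of 10 points (so 25% in Arm A), two-sided 5%, 80% power, 1:1 allocation, 20% non-compliance, no differential loss. Missing shares below are assumptions, because the protocol gives no rate of missing 12-month results. The 20% is borrowed from the non-compliance allowance.

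**The plan's own figure.** A continuity-corrected two-proportion calculation for 35% against 25% gives 349 per arm, as stated. Then 349 × 1.15 = 401.35 and 401.35 × 1.20 = 481.6, rounded up to 482. Two arms and the doubling for recurrent tumours give 482 × 4 = 1,928. So there are 482 per arm in the primary-tumour subgroup and 964 per arm overall.

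**1. The classification rule, case by case**

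| Seen before month 12 | Month 12 | Later | Score under 5.4 | Recurrence by 12 months? |
|---|---|---|---|---|
| Confirmed recurrence | missing | clear | none | yes |
| Confirmed recurrence | missing | not clear or no visit | recurrence | yes |
| Clear to month 9 | missing | clear | none | not seen |
| Clear to month 9 | missing | recurrence or no visit | recurrence | unknown |

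The first row contradicts observed data if the endpoint is cumulative. The last row assigns an event that was not observed by month 12.

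*Size of the erasure.* Let q be the share of true by-12-month recurrences that miss month 12 and are clear later. Counted rates become p(1 − q). At an assumed q = 10%: 0.25 × 0.9 = 22.5% and 0.35 × 0.9 = 31.5%, a difference of 9.0 points instead of 10.

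**2. Remaining gaps scored as recurrence, equal loss**

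Let m be the share missing with no later clear result. The imputed rate is p(1 − m) + m, so the difference is 10 × (1 − m) points.

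- m = 5%: 9.5 points
- m = 10%: 9.0 points
- m = 15%: 8.5 points
- m = 20%: 0.25 × 0.8 + 0.2 = 40% against 0.35 × 0.8 + 0.2 = 48%, or 8.0 points

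Power at m = 20% (normal approximation, no continuity correction) is 71% under the rule against 86% on observed cases with 482 per arm. With 964 per arm it is 94% against 99%.

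**3. Unequal loss, 964 per arm, 25% against 35% observed**

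| Missing A | Missing B | Imputed A | Imputed B | B − A |
|---|---|---|---|---|
| 10% | 20% | 32.5% | 48.0% | 15.5 points |
| 20% | 10% | 40.0% | 41.5% | 1.5 points (p = 0.50) |
| 30% | 10% | 47.5% | 41.5% | −6.0 points (p = 0.008) |

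The direction of the shift depends on which arm loses more patients.

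**4. The scenario that the rule leaves out**

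Take equal loss m, with missing scored as recurrence in Arm A and as no recurrence in Arm B. The difference is 0.35(1 − m) − [0.25(1 − m) + m] = 0.10 − 1.10m. It is zero at m = 0.10 / 1.10 = 9.1%.

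| m | Worst case for SPIES | Protocol's rule |
|---|---|---|
| 5% | +4.5 points | +9.5 points |
| 10% | −1.0 point | +9.0 points |
| 15% | −6.5 points | +8.5 points |
| 20% | −12.0 points | +8.0 points |

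**The case against.** The strongest reply is that this is a sensitivity analysis. Section 5.4 says so, and nothing in the rule enters the main estimate. That stands: lower power in the check does not bias the primary result. Scoring missing as recurrence in both arms is also a conventional cautious check when loss is balanced, as section 2.5 assumes. Section 3.3 blinds patients, and follow-up is white-light cystoscopy in both arms.

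A second reply is that the text permits the erasure without requiring it. If the endpoint is cumulative, a patient with a confirmed recurrence at month 6 is arguably not missing, so the rule never applies. That is fair, but the protocol does not say which reading holds, and section 5.4 handles each time point separately. The ambiguity is part of the fault.

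Third, a statistical analysis plan is foreseen in section 7.2 and may hold the main missing-data method and further scenarios. Their absence here is therefore not a finding. A rule written into the protocol can still be faulted for what it states.

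Four stronger readings are tempting, and the documents do not support them:

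- *The rule always shrinks the difference.* It does so under roughly equal loss. Unequal loss can enlarge or reverse it (step 3).
- *The rule cannot overturn a result.* It can. With 30% against 35%, 964 per arm and 20% missing in each, p moves from 0.036 on observed cases to 0.078 under the rule.
- *Patients found to have no tumour become events.* Nothing says so. If they attend and are clear, they are not missing, and section 5.4 limits the analysis to patients who met the entry criteria.
- *A clear patient who recurs at month 30 is always back-dated to month 12.* This happens only if month 12 is missed and months 18 and 24 give no clear result either.

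**Conclusion.** The point holds within these limits. The 12-month rule consults only later visits, so as written it allows a confirmed recurrence before month 12 to be scored as none, and it scores as 12-month events patients who were clear at month 9 and have no clear result from month 12 on. How many patients this touches cannot be known from the protocol. At an assumed 10% of recurrences erased, the difference falls from 10 to 9 points.

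For the remaining gaps, under the protocol's own assumption of no differential loss, the difference shrinks by (1 − m), to 8 points at an assumed 20%. The cost in power is moderate in the primary-tumour subgroup (86% to 71%) and small overall (99% to 94%).

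The main limitation of the check is that it imposes the same assumption on both arms. The worst case for SPIES would reverse a 10-point benefit once more than about 9% are missing in each arm, and the stated check would still show about 9 points in favour of SPIES. That worst case is extreme. It marks the edge of the range to be explored and is not a forecast.

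**What to change.** In section 5.4, with matching wording in 3.1.1 and 5.1:

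1. State that the primary endpoint is any histologically confirmed recurrence up to the end of the 12-month visit window.
2. Count such a recurrence as an event whatever is seen later, and whether or not month 12 was attended.
3. Count patients who are clear at or after month 12, with no earlier recurrence, as non-events.
4. For patients still unresolved, keep the missing-as-recurrence check and add a tipping-point analysis that varies the assumed recurrence risk of missing patients separately by arm, up to recurrence in Arm A and none in Arm B.
5. Report the share unresolved in each arm next to the results.

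The cost is one rewritten paragraph, an aligned endpoint definition and a little more analysis programming. No new data are needed, because the earlier and later visits are already scheduled and their lesions already sent for histology. The method for missing outcomes in the main analysis can stay with the statistical analysis plan.

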Rationale: Urothelial carcinoma of the bladder has a high recurrence rate, partly due to missed lesions at diagnostics with White Light Imaging (WLI) cystoscopy. Storz Professional Image Enhancement System (SPIES) is a new technique that visually enhances the images in order to improve diagnostic accuracy. SPIES assisted TURBs are expected to result in lower recurrence rates of bladder tumor compared with White Light TURBs.

Objective: To compare the recurrence rate of tumor at 12 months following SPIES assisted TURB with WLI assisted TURB in patients with non-muscle invasive bladder cancer (NMIBC Ta/T1/CIS).

Study design: This study is a multicenter randomized controlled trial in which the efficacy between SPIES assisted and WLI assisted TURB are compared. Subjects in the experimental arm (Arm A) will undergo SPIES assisted TURB, whereas subjects in the control arm (Arm B) will receive treatment with WLI assisted TURB only. Baseline characteristics will be recorded, as well as short and long-term follow up.

Study population: The study population comprises those patients who are presenting with primary or recurrent urothelial bladder cancer (NMIBC stage Ta, T1 or CIS) in the participating centers.

Intervention: All patients will undergo TURB. Patients in Arm A will undergo SPIES and WLI assisted TURB, and patients in Arm B will undergo WLI only assisted TURB.

Main study parameters/endpoints: Primary end point of the study is recurrence rate of tumor at 12 months after TURB in the two arms. Secondary end points include recurrence rates at 3 months and 3 years.

Nature and extent of the burden and risks associated with participation, benefit and group relatedness: The burden and risk associated with participating in this trial does not differ for patients in the experimental or the control arm. In both groups patients will undergo TURB, and will be followed for a maximum of three years at several site visits, in accordance with existing guidelines for follow up.

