2. OBJECTIVES

Primary Objective:

1. To compare the recurrence rate of tumor at 12 months following SPIES assisted TURB (Arm A) with White Light Imaging only assisted TURB (Arm B) in patients with primary or recurrent non-muscle-invasive urothelial bladder cancer (NMIBC Ta/T1/CIS). A subgroup analysis will be carried out for patients presenting with only primary tumors.

Secondary Objectives:

1. To assess the recurrence rate of tumor at short and long term follow up (3 months and 3 years) after SPIES or WLI assisted TURB in patients with NMIBC.
2. To assess the peri-operative morbidity (30 days) between SPIES and WLI assisted TURB by comparing the proportion of adverse events and using the Clavien-Dindo score.

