At three months after surgery, all patients will undergo a routine follow up using WLI cystoscopy. A two-week window will be allowed for the timing of this examination. All visible lesions should be confirmed histologically. Adjuvant treatment will be offered according to the local protocols. When appropriate, information on re-TUR and/or adjuvant treatment will be recorded, as well as adverse events. Information on re-TUR includes reasons for performing this procedure to determine if it was an incomplete resection or a true recurrence found at follow up. Information on adjuvant treatment includes type, timings, time limits and dose.

3.4.4 Intermediate follow up – 6, 9, 12, 18, 24 and 30 months after surgery – Visit 4 to 9

At the time points specified above, all patients will undergo a follow up using WLI cystoscopy. A four-week window will be allowed for the timing of this examination. All visible lesions should be confirmed histologically.

3.4.5 Last study follow up – three years after surgery – Visit 10

At three years after surgery, all patients will undergo a follow up using WLI cystoscopy. A four-week window will be allowed for the timing of this examination. All visible lesions should be confirmed histologically.

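### If three-year recurrence means any recurrence by 36 months, analysing it on available data overstates the rate in each arm; the protocol should define the endpoint and use an estimate that allows for censoring.

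*Protocol*

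**What the plan says.** The protocol Summary lists the endpoint as secondary: "Secondary end points include recurrence rates at 3 months and 3 years". Section 2 does the same in secondary objective 1: "To assess the recurrence rate of tumor at short and long term follow up (3 months and 3 years".

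Section 5.2 fixes the comparison: "The secondary end points of this trial will be tested in the same manner as described for the primary end point". Section 5.1 describes that manner as a two-sided test of equal proportions. Section 5.2 adds that appropriate tests will also be used for the different secondary objectives.

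Section 5.4 fixes the handling of missing data for these objectives: "In the analyses of secondary objectives, analyses will be carried out on available data, with reporting of proportions of missing data".

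Three other statements bear on the same data:

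- Section 3.1.1 puts three years inside the main endpoint: "histologically confirmed recurrence found at either three months, one year and three years after TURB".
- Section 5.4 has a sensitivity analysis for missing values of the primary outcome variable. It replaces a missing three-year result by recurrence.
- Section 5.4 also says that every eligible, consenting, randomised patient enters the analysis.

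Follow-up is by white-light cystoscopy at 3, 6, 9, 12, 18, 24, 30 and 36 months (sections 3.4.3 to 3.4.5 and 3.4.8).

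**The concern.** A recurrence at month 6 settles whether a patient has recurred by month 36, whatever happens later. A clear cystoscopy at month 18 does not. Take three patients under an available-data rule, with the endpoint read as any recurrence by 36 months:

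1. Recurrence confirmed at month 6, lost at month 20: outcome known, counted as an event.
2. Clear through month 18, lost at month 20: outcome unknown, removed from the denominator.
3. Clear at all eight visits: counted as no recurrence.

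Whether a lost patient is counted then depends on the outcome. The reported figure is observed recurrences divided by observed recurrences plus recurrence-free completers, which is larger than the three-year risk. This happens even when loss has nothing to do with prognosis. At stake is the trial's only long-term efficacy figure.

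**Working it through.** **Design figures.** The protocol gives no three-year recurrence rate and no three-year loss rate. Its own figure, from section 2.5, is 349 per arm for 35% against 25% at one year, two-sided 5%, power 80%, continuity-corrected.

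- Uncorrected: n = [1.96·√(2·0.30·0.70) + 0.8416·√(0.35·0.65 + 0.25·0.75)]² / 0.10² ≈ 328.5.
- Corrected: (328.5/4)·[1 + √(1 + 4/(328.5·0.10))]² ≈ 348.2, so 349. The figure reproduces.
- After inflation the protocol total is 1,928, or 964 per arm.

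**Inputs for the check.**

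- From the protocol: one-year recurrence 35% (B) and 25% (A); the eight visit times.
- Assumed: three-year recurrence 55% (B) and 45% (A), with 45/35 and 65/55 also run; constant hazard from 0 to 12 months and from 12 to 36 months; constant loss rate, independent of recurrence; no deaths.
- Loss of 10% to 40% by 36 months. The 20% case borrows the size of the section 2.5 non-compliance allowance, which is not a loss rate.

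**Formula (any recurrence by 36 months).** Let S be the probability of being recurrence-free and G the probability of still being followed. At visit k, the recurrences seen are (S at visit k−1 minus S at visit k) × G at visit k. Let E be their sum over visits, and C = S(36)·G(36) the recurrence-free completers. The available-data proportion is E/(E + C).

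**Arm B, 20% loss:**

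| Month | Drop in S | G | Product |
|---|---|---|---|
| 3 | 0.1021 | 0.9816 | 0.1002 |
| 6 | 0.0917 | 0.9635 | 0.0883 |
| 9 | 0.0823 | 0.9457 | 0.0778 |
| 12 | 0.0739 | 0.9283 | 0.0686 |
| 18 | 0.0571 | 0.8944 | 0.0511 |
| 24 | 0.0521 | 0.8618 | 0.0449 |
| 30 | 0.0475 | 0.8303 | 0.0394 |
| 36 | 0.0433 | 0.8000 | 0.0347 |

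E = 0.505 and C = 0.45·0.80 = 0.360, so E/(E + C) = 0.505/0.865 = 58.4%, against a true 55%. The dropped share is 1 − 0.865 = 13.5%, all with no recurrence found when last seen. For arm A, E = 0.409 and C = 0.55·0.80 = 0.440, giving 48.2% against a true 45%, with 15.1% dropped.

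**Equal loss in both arms (true 55% and 45%, difference 10.0):**

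| Loss | B reported | A reported | Difference |
|---|---|---|---|
| 10% | 56.6 | 46.5 | 10.1 |
| 20% | 58.4 | 48.2 | 10.2 |
| 30% | 60.4 | 50.1 | 10.3 |
| 40% | 62.8 | 52.5 | 10.3 |

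Over 45/35 and 65/55 as well, the overstatement runs from about 1.3 to 9 points, and the difference still moves by less than 1 point.

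**Unequal loss, no true effect (55% in both arms).**

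- 15% loss: 0.517/(0.517 + 0.3825) = 57.5%.
- 25% loss: 0.493/(0.493 + 0.3375) = 59.4%.
- False difference: 1.9 points.
- Evaluable: 964·0.899 ≈ 867 and 964·0.831 ≈ 801.
- SE = √(0.575·0.425/867 + 0.594·0.406/801) = 0.0241; shift = 0.0191/0.0241 = 0.79.
- Two-sided rejection = Φ(0.79 − 1.96) + Φ(−0.79 − 1.96) ≈ 12%.
- At 10% against 30% loss, the false difference is 3.8 points and rejection about 35%.

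**Estimate with censoring.** Among patients still followed at visit k, the proportion remaining clear is S at visit k over S at visit k−1. The product over eight visits is 0.45 (B) and 0.55 (A), so the estimates are 55% and 45%, whatever the independent loss.

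**Status at the 36-month visit.** Only attenders count, so patients 1 and 2 above both drop out. Independent loss then causes no overstatement.

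**Sensitivity rule, missing counted as recurrence.** At 20% loss it gives 1 − 0.360 = 64% (B) and 1 − 0.440 = 56% (A). That is higher than the available-data figures, so it does not correct them.

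**The case against.** The strongest objection is to the premise. A reader might infer that the protocol itself keeps a patient lost after a recurrence as an event. No sentence says so. The wording in section 3.1.1 fits status at the visit as well as cumulative recurrence, and the substitution rules in section 5.4 look forward to later results and never carry an earlier recurrence forward. This stands: the overstatement is conditional on the cumulative reading.

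The text still leans towards that reading. Letting a later clear result fill a missing 12-month result makes sense only if status carries over time, and section 1 justifies the technique by fewer invasive procedures. The alternative has its own cost: a recurrence found and treated at month 6 would count as none if month 36 is clear.

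A reader might also infer that the treatment comparison is biased. The documents do not support this. Section 2.5 assumes no differential loss, section 3.3 blinds patients, and both arms have the same follow-up. The unequal-loss figures are illustrations, not predictions.

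Nor is available data the only stated treatment of three-year results, given the missing-as-recurrence rule and the listing in section 3.1.1. That makes reconciliation part of the point.

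Finally, section 5.2 allows other appropriate tests, and section 7.2 foresees an analysis plan that may settle the details. However, the available-data rule is stated in the protocol and is not left open there.

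**Conclusion.** The point holds conditionally. Under the cumulative reading, the available-data rule overstates three-year recurrence in each arm by about 3 points at 20% loss and about 1.5 to 8 points at 10% to 40% loss. This rests on assumed risks of 55% and 45%, independent loss and no deaths. With equal loss the between-arm difference is nearly unaffected. Material distortion needs unequal loss, which nothing in the protocol predicts. Under the status-at-visit reading there is no overstatement from independent loss, but earlier treated recurrences go uncounted. The protocol does not choose between the readings, and its sections disagree on whether three years is main or secondary and which missing-data rule applies. The 12-month comparison is not affected by this point. The change should be made because it gives a better-defined long-term result at little cost.

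**What to change.** In sections 5.2 and 5.4, replace the available-data comparison for three-year recurrence with wording such as:

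*Three-year recurrence is the cumulative incidence of first histologically confirmed recurrence by 36 months, using all scheduled follow-up cystoscopies. Patients lost without recurrence are censored at their last clear cystoscopy. Death without recurrence is a competing event, and the Aalen-Johansen estimator is used. Arms are compared by the difference at 36 months with a 95% confidence interval, stratified by the randomisation factors.*

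If deaths are to be censored instead, use Kaplan-Meier and say so. Kaplan-Meier does not treat death as a competing event, so the two should not be combined. Keep the available-data proportion as descriptive only.

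Reconcile the Summary and sections 2, 3.1.1 and 5.4: state whether three years is a main or a secondary endpoint, and whether available data or missing-as-recurrence applies to it. The available-data denominator must also be squared with the statement that all eligible randomised patients are analysed.

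The cost is a few sentences and a standard survival analysis. No visits, data or patients are added. The downside is that the estimate assumes loss is non-informative within arm and stratum.
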